## **11 STUDY MANAGEMENT AND ADMINISTRATION**

### **11.1 Adherence to protocol**

The Investigator should not deviate from the protocol. However, the Investigator should take any measure necessary in deviation from or not defined by the protocol in order to protect clinical study participants from any immediate hazard to their health and safety. In this case, this action should be taken immediately, without prior notification of the regulatory authority, IEC, or Sponsor.

After implementation of such measure, the Investigator must notify the Exploratory Project Manager of the Sponsor within 24 hours and follow any local regulatory requirements.

### **11.2 Monitoring**

UCB (or designee) will monitor the study to meet the Sponsor's monitoring SOPs, ICH-GCP guideline, and applicable regulatory requirements, and to ensure that study initiation, conduct, and closure are adequate. Monitoring of the study may be delegated by UCB to a CRO or a contract monitor.

The Investigator and his/her staff are expected to cooperate with UCB (or designee) and to be available during the monitoring visits to answer questions sufficiently and to provide any missing information. The Investigator(s)/institution(s) will permit direct access to source data/documents for study-related monitoring, audits, IEC review, and regulatory inspection(s).

The Investigator will allow UCB (or designee) to periodically review all eCRFs and corresponding source documents (eg, hospital and laboratory records for each study participant). Monitoring visits will provide UCB (or designee) with the opportunity to evaluate the progress of the study, verify the accuracy and completeness of eCRFs, ensure that all protocol requirements, applicable authorities regulations, and Investigator's obligations are being fulfilled, and resolve any inconsistencies in the study records.

#### **11.2.1 Definition of source data**

All source documents must be accurate, clear, unambiguous, permanent, and capable of being audited. They should be made using some permanent form of recording (ink, typing, printing, optical disc). They should not be obscured by correction fluid or have temporary attachments (such as removable self-stick notes).

Source documents are original records in which raw data are first recorded. These may include hospital/clinic/general practitioner records, charts, diaries, x-rays, laboratory results, printouts, pharmacy records, care records, ECG or other printouts, completed scales, or quality of life questionnaires, for example. Source documents should be kept in a secure, limited access area.

Source documents that are computer generated and stored electronically must be printed for review by the monitor (eg, ECG reports). Once printed, these copies should be signed and dated by the Investigator and become a permanent part of the study participant's source documents.

The Investigator will facilitate the process for enabling the monitor to compare the content of the printout and the data stored in the computer to ensure all data are consistent.

Electronic data records, such as Holter monitor records or electroencephalogram records, must be saved and stored as instructed by UCB (or designee).

### **11.2.2 Source data verification**

Source data verification ensures accuracy and credibility of the data obtained. During monitoring visits, reported data are reviewed with regard to being accurate, complete, and verifiable from source documents (eg, study participant files, recordings from automated instruments, tracings [ECG], x-ray films, laboratory notes). All data reported on the eCRF should be supported by source documents, unless otherwise specified in [Section 11.2.1](#).

## **11.3 Data handling**

### **11.3.1 Case Report form completion**

The Investigator is responsible for prompt reporting of accurate, complete, and legible data in the eCRFs and in all required reports.

Any change or correction to the eCRF after saving must be accompanied by a reason for the change.

Corrections made after the Investigator's review and approval (by means of a password/electronic signature) will be reapproved by the Investigator.

The Investigator should maintain a list of personnel authorized to enter data into the eCRF.

Detailed instructions will be provided in the eCRF Completion Guidelines.

### **11.3.2 Database entry and reconciliation**

Electronic Case Report forms/external electronic data will be entered/loaded into a validated electronic database using a clinical data management system (CDMS). Computerized data cleaning checks will be used in addition to manual review to check for discrepancies and to ensure consistency of the data. Case Report form data are entered into the clinical database using independent, double-data entry, with the exception of comment fields, which are verified by a second person. The data are entered into the eCRFs once and are subsequently verified if the study is performed using electronic data capture.

An electronic audit trail system will be maintained within the CDMS to track all data changes in the database once the data have been saved initially into the system or electronically loaded. Regular backups of the electronic data will be performed.

### **11.3.3 Study Participant Screening and Enrollment log/Study Participant Identification Code list**

The study participant's screening and enrollment will be recorded in the Study Participant Screening and Enrollment Log.

The Investigator will keep a Study Participant Identification Code list. This list remains with the Investigator and is used for unambiguous identification of each study participant.

The study participant's consent and enrollment in the study must be recorded in the study participant's medical record. These data should identify the study and document the dates of the study participant's participation.

## **11.4 Termination of the study**

UCB reserves the right to temporarily suspend or prematurely discontinue this study either at a single site, multiple sites, or at all sites at any time for reasons including, but not limited to, safety or ethical issues, inaccurate or incomplete data recording, noncompliance, or unsatisfactory enrollment with respect to quality or quantity.

If the study is prematurely terminated or suspended, UCB (or its representative) will inform the Investigators/institutions and the regulatory authority(ies) of the termination or suspension and the reason(s) for the termination or suspension, in accordance with applicable regulatory requirement(s). The IEC should also be informed and provided with reason(s) for the termination or suspension by the Sponsor or by the Investigator/institution, as specified by the applicable regulatory requirement(s). In addition, arrangements will be made for the return of all unused IMP and other material in accordance with UCB procedures for the study.

## **11.5 Archiving and data retention**

The Investigator will maintain adequate records for the study, including eCRFs, medical records, laboratory results, Informed Consent documents, drug dispensing and disposition records, safety reports, information regarding participants who discontinued, and other pertinent data.

All essential documents are to be retained by the Investigator until at least 2 years after the last approval of a marketing application in an ICH region and until there are no pending or contemplated marketing applications in an ICH region, or at least 2 years have elapsed since the formal discontinuation of clinical development of the IMP. These documents should be retained for a longer period, however, if required by the applicable regulatory requirement(s) or by an agreement with UCB (Committee for Proprietary Medicinal Products [CPMP]/ICH/135/95, 2002 [Section 4.9.5]). The Investigator will contact UCB for authorization prior to the destruction of any study records or in the event of accidental loss or destruction of any study records. The Investigator will also notify UCB should he/she relocate or move the study-related files to a location other than that specified in the Sponsor's Study Master File.

## **11.6 Audit and inspection**

The Investigator will permit study-related audits mandated by UCB, after reasonable notice, and inspections by domestic or foreign regulatory authorities.

The main purposes of an audit or inspection are to confirm that the rights and wellbeing of the study participants enrolled have been protected, that enrolled study participants (ie, signing consent and undergoing study procedures) are appropriate for the study, and that all data relevant for the evaluation of the IMP have been processed and reported in compliance with the planned arrangements, the protocol, investigational site, and IEC SOPs, ICH GCP, and applicable regulatory requirements.

The Investigator will provide direct access to all study documents, source records, and source data. If an inspection by a regulatory authority is announced, the Investigator will immediately inform UCB (or designee).

## **11.7 Good Clinical Practice**

Noncompliance with the protocol, ICH-GCP, or local regulatory requirements by the Investigator, institution, institution staff, or designees of the Sponsor will lead to prompt action

by UCB to secure compliance. Continued noncompliance may result in the termination of the site's involvement in the study.

## **12 STATISTICS**

A description of statistical methods follows and will be described in more detail in the Statistical Analysis Plan (SAP).

### **12.1 Definition of analysis sets**

#### **12.1.1 Enrolled Set**

The Enrolled Set (ES) consists of all study participants who have signed the ICF.

#### **12.1.2 Full Analysis Set**

The Full Analysis Set (FAS) consists of all study participants who have signed the ICF form and received IMP. Analysis of this set will be according to the treatment the study participants actually received.

All safety analyses will be performed using the FAS. All safety variables will be summarized by treatment (PSL alone, erythromycin alone, PSL+erythromycin, and the SFU).

#### **12.1.3 Pharmacokinetic Per-Protocol Set**

The Pharmacokinetic Per-Protocol Set (PK-PPS) is a subset of the FAS, consisting of those study participants who had no important protocol deviations affecting the PK parameters and for whom a sufficient number of samples are available to determine at least 1 PK parameter.

### **12.2 General statistical considerations**

Summary statistics will be provided for all safety and Baseline/demographic variables. The datasets will follow the UCB analysis data model (ADaM) data specifications. All analyses will be performed using SAS® version 9.4 or later (SAS Institute, Cary, NC, USA). The PK noncompartmental analysis (NCA) will be performed using Pharsight Phoenix® WinNonlin® v6.3 (or higher). Categorical endpoints will be summarized using number of participants, frequency, and percentages. Missing data will not be imputed. For continuous variables, descriptive statistics (number of available observations, mean, median, standard deviation [SD], minimum, and maximum) will be tabulated.

### **12.3 Planned pharmacokinetic and other analyses**

#### **12.3.1 Analysis of the primary pharmacokinetic variables**

Pharmacokinetics will be determined using the PK-PPS.

Pharmacokinetic parameters of PSL and metabolites will be calculated by using the actual blood sampling time points.

The plasma concentration time profiles (and urine amounts) and PK parameters of PSL and metabolites will be summarized by treatment periods using descriptive statistics (number of available observations, arithmetic mean, SD, geometric mean, coefficient of variation of the geometric mean, median, minimum, and maximum). Values below the lower limit of quantification (LLOQ) will be reported with a clear sign indicating that they were below the

LLOQ. Descriptive statistics of concentrations will be calculated if at least two-thirds of the individual data points are quantifiable ( $\geq$ LLOQ).

Individual plasma PSL and metabolites concentration time profiles will be displayed graphically on a linear-linear scale and semi-logarithmic scale (including spaghetti plots). Geometric mean plasma concentrations-time curves including 95% confidence intervals (CIs) will be displayed by treatment period (without/with erythromycin).

The similarity of PK parameters for PSL and its metabolites ( $C_{max}$ ,  $AUC_{(0-12)}$ ,  $C_{max,ss}$ , and  $AUC_{\tau}$ ) between periods with erythromycin and without erythromycin will be assessed within the analysis of variance (ANOVA) using data from the 3 treatment periods as follows: point estimates for the ratio of geometric means between with and without erythromycin and the respective 2-sided 90% CIs will be computed using the least squares means and the root mean squares of error from the ANOVA of the log-transformed data with subsequent exponential transformation. Inter-study participant and intra-study participant variability on PK parameters for PSL and its metabolites will be derived from these analyses. Ping pong plots will be displayed.

The PSL concentrations and PK parameters obtained from MITRA microsampling method will be compared to those of the conventional venous sampling method using descriptive analysis (tables with summary statistics and graphs).

### 12.3.2 Safety analyses

All safety analyses will be performed using the study participants in the FAS.

All AEs will be coded using the Medical Dictionary for Regulatory Activities (MedDRA®) and characterized as pre-treatment and treatment-emergent according to the intake of the IMP.

The occurrence and incidence of treatment-emergent adverse events (TEAEs) will be summarized by MedDRA system organ class and preferred term, by treatment periods, by treatment, and by treatment within treatment periods (for Treatment Period 3b). The occurrence and incidence of TEAEs will also be summarized by intensity and by relationship to the IMP as judged by the Investigator. Adverse events leading to discontinuation and SAEs will also be summarized.

Laboratory variables and changes from Baseline (during the Screening Period) will be summarized by descriptive statistics at each time point by treatment periods. Shift tables from Baseline to each post-Baseline time point will be presented by treatment periods. Values outside the reference range will be flagged in the listings. Any PDILI events will be listed.

Vital sign variables (BP, PR, oral body temperature, and respiration rate) and changes from Baseline (predose of each treatment period) will be summarized by descriptive statistics at each time point by treatment periods.

Electrocardiograms will be recorded 3 times at each time point. The individual mean at each time point will be calculated as raw parameters for descriptive analysis. The individual mean and change from baseline (time-matched Baseline day of each treatment period, when applicable) will be summarized by descriptive statistics at each time point by treatment periods.

Physical examination abnormalities and C-SSRS data will be listed.

## **12.4 Handling of protocol deviations**

Important protocol deviations (IPDs) are deviations from the protocol that potentially could have a meaningful impact on the primary objective of the study. The criteria for identifying such protocol deviations will be defined within the relevant protocol deviation specification document, which is part of the data cleaning plan. The IPDs will be reviewed as part of the ongoing data cleaning process and data evaluation. After all data have been verified/coded/entered into a database, a data evaluation meeting (DEM) will be performed. The purpose of this review will be to check all protocol deviations and the quality of the data. The review will also help guide the decision how to manage problems in the study participants' data (eg, withdrawals, dropouts, and protocol deviations).

Accepted deviations from theoretical time points will be described in the appropriate documents and included in the Study Master File. After the data review, resolution of all issues, and documentation of all decisions, the database will be locked.

## **12.5 Handling of dropouts or missing data**

The methods for handling dropouts and missing data will be described in the SAP.

## **12.6 Planned interim analysis and data monitoring**

There is no interim analysis planned for this study.

## **12.7 Determination of sample size**

Using SimCYP simulations data, a sample size of 20 healthy study participants is needed to assess the PK interaction between PSL and erythromycin, and to estimate the mean PSL  $AUC_{\tau}$  ratio of with/without erythromycin of 3.2 with a half-width of the CI of 0.75.

This sample size has been evaluated with a conditional probability of 80%, assuming an inter-participant coefficient of variation of 140%, correlation of 0.5, 2-sided and  $\alpha = 0.05$ .

A sufficient number of healthy study participants (up to 28) will be selected to have 20 completed study participants.

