## 5.9 Rationale for study design and selection of dose

Padsevonil is being administered at a dose of 100mg bid to evaluate and compare the plasma and urine PK, as well as the safety and tolerability profile, of PSL in the presence and absence of erythromycin. The plasma and urine PK of the known metabolites of PSL will also be evaluated and compared in the presence and absence of erythromycin. This dose has been selected to ensure that safety margins are not exceeded following administration of PSL with a CYP3A4 inhibitor and that the effect of CYP2C19 auto-inhibition on PSL metabolism is achieved in addition to the overall effect of CYP3A4 inhibition. In addition, 100mg is 1 of the doses planned to be investigated in the dose-ranging study, EP0091. Erythromycin given at a dose of 500mg bid is expected to increase exposure to PSL by approximately 3.7-fold (SimCYP simulations).

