2.4 Determination of sample size

Using SimCYP simulations data, a sample size of 20 healthy study participants is needed to assess the PK interaction between PSL and erythromycin, and to estimate the mean PSL AUC_{τ} ratio of with/without erythromycin of 3.2 with a half-width of the confidence interval (CI) of 0.75.

This sample size has been evaluated with a conditional probability of 80%, assuming an inter-participant coefficient of variation of 140%, correlation of 0.5, 2-sided and $\alpha=0.05$.

A sufficient number of healthy study participants (up to 28) will be enrolled to have 20 completed study participants.

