The primary comparison of interest is the similarity of plasma PK parameters (C_{max} , $AUC_{(0-12)}$, $C_{max,ss}$, and AUC_{τ}) for PSL between treatment periods with erythromycin (Treatment Period 3b) and PSL without erythromycin (treatment periods 1 and 2). This will be assessed using a linear mixed effects model with treatment periods (1, 2 and 3b, comparing with vs without erythromycin periods) fitted as fixed effects and subject fitted as a random effect. The mixed effects model will be using Kenward-Rodgers degrees of freedom. Point estimates for the ratio of geometric means with and without erythromycin (Period 3b compared to periods 1 and 2) and the respective 2 sided 90% CIs will be computed using the least squares means and the root mean squares of error from the mixed effects model, based on of the log-transformed data with subsequent exponential transformation. In addition point estimates for the ratio of geometric means and the respective 2 sided 90% CIs will be presented for the following comparisons:

- Treatment Period 1 (PSL) compared to Treatment Period 3b (PSL + erythromycin)
- Treatment Period 2 (PSL) compared to Treatment Period 3b (PSL + erythromycin)

Treatment Period 1 (PSL) compared to Treatment Period 2 (PSL) Ping pong plots will be displayed for each of the PK parameters (C_{max} , $AUC_{(0-12)}$, $C_{max,ss}$, and AUC_{τ}) against treatment of PSL with (Treatment Period 3b) and without erythromycin (treatment periods 1 and 2, separately).

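### The sample-size precision statement (ratio 3.2, half-width 0.75, CV 140%, n = 20) does not hold for the planned log-scale analysis, and its scales are not stated

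*Protocol*

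**What the plan says.** Protocol 12.7 states that "a sample size of 20 healthy study participants is needed to assess the PK interaction between PSL and erythromycin", and to estimate the mean AUCtau "ratio of with/without erythromycin of 3.2 with a half-width of the CI of 0.75". The calculation uses a conditional probability of 80%, "assuming an inter-participant coefficient of variation of 140%, correlation of 0.5, 2-sided and" alpha 0.05. Up to 28 participants may be taken in to obtain 20 completers. SAP 2.4 repeats the same figures ("ratio of with/without erythromycin of 3.2 with a half-width of the confidence interval (CI) of 0.75").

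The planned analysis is on the log scale. Protocol 12.3.1 takes the estimates "from the ANOVA of the log-transformed data with subsequent exponential transformation". SAP 9.1 fits a mixed model to the three PSL periods, "comparing with vs without erythromycin periods) fitted as fixed effects and subject fitted as a random effect", and "the respective 2 sided 90% CIs will be computed using the least squares means and the root mean squares of error".

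Protocol 5.9 says that erythromycin is "expected to increase exposure to PSL by approximately 3.7-fold (SimCYP simulations".

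**The concern.** The sample-size text mixes a ratio, a half-width, a CV and a correlation without giving the scale of any of them. Read as written, it promises that the AUCtau ratio will be known to about 3.2 ± 0.75, that is 2.45 to 3.95, with 80% probability. A CV of 140% is very large, and 20 participants look too few for that.

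This is the only justification given for the size of the trial, and the trial is sized on precision. If the statement is wrong, readers will expect a much tighter estimate of the interaction than the design can give.

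**Working it through.** **Inputs** (Protocol 12.7): n = 20, ratio 3.2, half-width 0.75, probability 80%, CV 140%, correlation 0.5, two-sided alpha 0.05. Analysis (Protocol 12.3.1, SAP 9.1): log scale, three periods, 90% CI.

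**1. Reproducing n = 20.** For a paired comparison, half-width = t(0.975, n−1) × SD × √(2(1−r)/n). The half-width met with 80% probability multiplies this by √(χ²₀.₈(n−1)/(n−1)). With SD = 1.4 and r = 0.5, the SD of the difference is 1.4.

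- n = 19: 80%-probability half-width 0.759. The probability of 0.75 or less, given that the CI covers the true value, is 76.9%.
- n = 20: 0.735 and 82.9%.

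So 20 follows exactly if 140% is used directly as an SD of 1.4 in the same units as the 0.75. On the log scale, however, an SD of 1.4 is a CV of √(exp(1.96) − 1) = 247%, not 140%.

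**2. Converting the CV.** Log SD = √ln(1 + 1.4²) = √ln 2.96 = 1.042. If the 0.5 is a raw-scale correlation, the log-scale value under lognormality is ln(1 + 0.5 × 1.96)/ln 2.96 = 0.629. Results below are given for r = 0.5 and r = 0.629.

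**3. If 0.75 is in log units.** The interval is 3.2 × exp(±0.75) = 1.51 to 6.77. Conditional on coverage, this needs 13 completers (r = 0.5) or 11 (r = 0.629; n = 10 gives 79.4%).

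**4. If 0.75 is in ratio units.** Half the width of the back-transformed CI is 3.2 × sinh(h), where h is the log half-width. Reaching 0.75 therefore needs h ≤ asinh(0.75/3.2) = 0.232.

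For the planned model, assume one common correlation between all three periods. The contrast of Period 3b with the mean of Periods 1 and 2 then has SE = √(1.5 × SD² × (1−r)/n), with 2(n−1) = 38 degrees of freedom and t = 1.686.

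| At n = 20 | r = 0.5 | r = 0.629 |
|---|---|---|
| Paired, 95%: expected CI | 1.97 to 5.21 | 2.10 to 4.87 |
| Half-width (with 80% probability) | 1.62 (1.84) | 1.38 (1.56) |
| Chance of 0.75 or less | 0.02% | 0.17% |
| Completers needed | 90 | 68 |
| Planned model, 90%: expected CI | 2.28 to 4.50 | 2.39 to 4.29 |
| Half-width (with 80% probability) | 1.11 (1.21) | 0.95 (1.04) |
| Chance of 0.75 or less | 0.2% | 3.6% |
| Completers needed | 47 | 36 |

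The chances in the table are not conditioned on coverage; conditioning makes them slightly smaller and leaves the required numbers unchanged. A simulation of the planned model with 20,000 trials gave 0.24% and 3.4%. With all 28 participants completing, the planned model gives an expected half-width of 0.93 or 0.79. For 0.75 to be met at n = 20 with 80% probability, the CV would have to be about 47% to 48% (paired, 95%) or 73% to 79% (planned model, 90%).

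**5. A raw-scale route to 20.** Take means of 1 and 3.2, SD 1.4 in both periods and r = 0.5. The SD of the difference is √(1.96 + 1.96 − 1.96) = 1.4, which again gives 20. But the CV with erythromycin is then 1.4/3.2 = 44%. With a CV of 140% in both periods the SDs are 1.4 and 4.48, the SD of the difference is √(1.96 + 20.07 − 6.27) = 3.97, and 122 completers are needed.

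**The case against.** The strongest reply is that 20 is not a calculation error. The stated numbers give exactly 20 when 1.4 is used as an SD, and the disagreement appears only after a CV-to-SD conversion that the protocol does not mention. The two readings of 0.75 also point in opposite directions: in log units 20 is more than enough, and only in ratio units is it too few. The sponsor's own calculation might settle this. Moreover, no decision rule depends on 0.75.

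Much of this is fair. The number 20 can be reproduced, the cause cannot be established from the documents, and the intended scale is unknown. The objection does not rescue the statement. The planned analysis is on the log scale, and an SD of 1.4 there contradicts the stated CV. The raw-scale route contradicts it in the period with erythromycin. The sentence attaches the half-width directly to a ratio of 3.2, so readers will take it in ratio units.

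A further reservation is that the planned-model figures apply a single correlation to all period pairs, while the protocol gives one value without saying which pairs it covers. A random subject effect implies a common correlation in the fitted model, but as a planning value it remains an assumption. The paired figures do not depend on it and are less favourable.

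**Conclusion.** The concern holds. Under the stated CV and correlation, no reading of the 0.75 gives 20 completers for the planned log-scale analysis. On the natural, ratio-scale reading the expected half-width is 0.95 to 1.11 (planned model, 90% CI) or 1.38 to 1.62 (paired, 95% CI). The chance of reaching 0.75 is at most 3.6%, against the stated 80%. These figures assume lognormal data and, for the planned model, a common correlation; the ranges cover a correlation of 0.5 on either the log or the raw scale.

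The consequence is limited. The expected 90% CI from the planned model excludes both 1 and 2, so the trial can still show and broadly quantify the interaction. What is wrong is the stated precision. It should be corrected, but it does not call for a larger trial.

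**What to change.** Keep n = 20. The sponsor should confirm from its own calculation which scale was used for the SD and the correlation. In Protocol 12.7 and SAP 2.4, delete the 0.75 half-width and state the precision of the planned analysis, keeping whichever one of the two intervals applies. For example:

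> With 20 completers, a CV of 140% (log SD 1.04) and a log-scale correlation of 0.5 between all periods, the expected 90% CI for a ratio of 3.2 from the three-period model is about 2.28 to 4.50 (2.39 to 4.29 if the correlation of 0.5 is on the raw scale).

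Two smaller points can be settled in the same edit. The planning alpha of 0.05 implies a 95% CI, while the analysis reports 90% CIs; the mismatch is conservative, but the levels should be aligned. The documents should also say whether the simulated ratio of 3.2 in Protocol 12.7 and the 3.7-fold increase in Protocol 5.9 are the same quantity, and reconcile them if so.

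The cost is wording in two sections, plus the clarification of the 3.7-fold figure. No participants are added and the analysis does not change. The stated precision becomes less favourable than ±0.75.
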